### 7.3 Pregnancy Reporting

Pregnancy is neither an AE nor an SAE, unless a complication relating to the pregnancy occurs (e.g., spontaneous abortion, which may qualify as an SAE).

Pregnancies and suspected pregnancies (including a positive pregnancy test regardless of age or disease state) of a female participant or partner of a male participant occurring while the participant is on study treatment, within 28 days or during at least 5 til2 after product administration of the participant's last dose of study treatment, are considered immediately reportable events. If a female partner of a male participant taking investigational product becomes pregnant, the male participant taking study treatment should notify the Investigator, and the pregnant female partner should be advised to call her healthcare provider immediately. In pregnant female participants, study treatment is to be discontinued immediately and the participant instructed to return any unused study drug to the Investigator. The pregnancy, suspected pregnancy, or positive pregnancy test must be reported immediately to the Lead PI. The Investigator must follow-up and document the course and outcome of all pregnancies even if the participant was discontinued from the study or if the study has finished. The female participant or partner of a male participant should receive any necessary counseling regarding the risks of continuing the pregnancy and the possible effects on the fetus. Monitoring should continue until conclusion of the pregnancy.

All outcomes of pregnancy (from a female participant or the sexual partner of a male participant) must be reported by the Investigator to the Lead PI as an SAE within 28 days after he/she has gained knowledge of the delivery or elective abortion.

Any SAE that occurs during pregnancy must be recorded on the SAE report form (eg, maternal serious complications, spontaneous or therapeutic abortion, ectopic pregnancy, stillbirth, neonatal death, congenital anomaly, or birth defect) and reported within 24 h in accordance with the procedure for reporting SAEs.

Females of reproductive potential must have a negative serum pregnancy test prior to the start of therapy, or a confirmation from an obstetrician in case of equivocal serum pregnancy results. Women of reproductive potential, as well as fertile men and their partners who are female with reproductive

potential, must agree to use two effective forms of contraception (including at least one barrier form) from the time of giving informed consent throughout the study and 7 months (both females and males) following the last dose of study drug. Women of reproductive potential are defined as sexually mature women who have not undergone a hysterectomy or bilateral oophorectomy or who have not been naturally postmenopausal (ie, who have not menstruated at all) for at least 24 consecutive months (ie, has had menses at any time in the preceding 24 consecutive months).

Men with partners who are women with reproductive potential must agree that they or their partners will use two effective forms of contraception (including at least one barrier form) when engaging in reproductive sexual activity throughout the study and will avoid conceiving 7 months after the last dose of study treatment.

Effective forms of contraception are defined as hormonal oral contraceptives, injectables, patches, intrauterine devices, intrauterine hormone-releasing systems, bilateral tubal ligation, condoms with spermicide, or male partner sterilization.

# 7.3.1 Specific BMS Pregnancy Reporting

If, following initiation of the investigational product, it is subsequently discovered that a study participant is pregnant or may have been pregnant at the time of investigational product exposure, including during at least 5 *ti12* after product administration, the investigational product will be permanently discontinued in an appropriate manner (eg, dose tapering if necessary for participant).

The investigator must immediately notify [contact] of this event in accordance with SAE reporting procedures.

Protocol-required procedures for study discontinuation and follow-up must be performed on the participant.

Follow-up information regarding the course of the pregnancy, including perinatal and neonatal outcome and, where applicable, offspring information must be reported.

Any pregnancy that occurs in a female study participant or a female partner of a male study participant should be reported to BMS. Information on this pregnancy will be collected. The female participant or female partner must sign an informed consent form for disclosure of this information.

### 7.4 Follow-up of Participants after AEs

### 7.4.1 Investigator Follow-Up

The Investigator should follow each AE until the event has resolved to baseline grade or better, the event is assessed as stable by the Investigator, the participant is lost to follow-up, or the participant withdraws consent. Every effort should be made to follow all SAEs considered related to study treatment or trial-related procedures until a final outcome can be reported.

### 7.4.2 Post-study Adverse Events

At the treatment discontinuation visit, the Investigator should instruct each participant to report to the Investigator any subsequent AEs that the participant's personal physician believes could be related to prior study treatment or study procedures.

The Investigator should notify the Sponsor of any death, SAE, or other AE of concern occurring at any time after a participant has discontinued study participation if the event is believed to be related to prior study treatment or study procedures. The Sponsor should also be notified if the Investigator

becomes aware of the development of cancer or a congenital anomaly/birth defect in a subsequently conceived offspring of a participant that participated in this study.

# 7.5 Definition of DLT

AEs will be graded according to the NCI CTCAE version 5.0.

A DLT is defined as any AE (except clearly attributable to an extraneous cause, such as disease progression) occurring in Cycle 1 (only) that satisfies at least one of the following criteria:

### Non-hematologic AEs:

- Grade 3 or 4 nausea or vomiting:
  - o If no anti-emetic prophylaxis was administered, Grade 3 or 4 nausea or vomiting is considered a DLT only if lasting> 3 days despite maximum supportive care.
  - o Grade 3 or 4 nausea or vomiting despite anti-emetic prophylaxis of any duration will be considered a DLT.
- Grade 3 or 4 diarrhea:
  - o If no anti-diarrheals were administered, Grade 3 or 4 diarrhea is considered a DLT only if lasting> 3 days despite maximum supportive care.
  - o Grade 3 or 4 diarrhea despite the administration of anti-diarrheals of any duration will be considered a DLT.
- Any other Grade 3 or 4 non-hematological AE, with the exception of asymptomatic amylase/lipase or other biochemical marker that does not resolve with adequate treatment and/or within a week.

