### 5.8 Nivolumab AEs

Nivolumab treatment should be permanently discontinued for the following:

Any Grade 2 drug-related uveitis, eye pain, or blurred vision that does not respond to topical therapy and does not improve to Grade 1 severity within the OR requires systemic treatment

Any Grade 3 non-skin, drug-related AE lasting> 7 days or recurs, with the following exceptions for laboratory abnormalities, diarrhea, drug-related uveitis, pneumonitis, bronchospasm, hypersensitivity reactions, infusion reactions, and endocrinopathies:

- Grade 3 drug-related diarrhea, uveitis, pneumonitis, bronchospasm, hypersensitivity reaction, or infusion reaction of any duration requires discontinuation.
- Grade 3 drug-related endocrinopathies adequately controlled with only physiologic hormone replacement do not require discontinuation.

- Grade 3 drug-related laboratory abnormalities do not require treatment discontinuation except for the following:
  - Grade 3 drug-related thrombocytopenia > 7 days or associated with bleeding requires discontinuation
  - o Any drug-related liver function test (LFT) abnormality that meets the following criteria require discontinuation:
    - Grade 3 drug-related AST, ALT, or total bilirubin requires discontinuation
    - Concurrent AST or ALT> 3x ULN and total bilirubin > 2x ULN

Any drug-related Grade 4 endocrinopathy and Grade 3 adrenal insufficiency requires discontinuation.

Any Grade 4 drug-related AE or laboratory abnormality (including but not limited to creatinine, AST, ALT, or total bilirubin), except for the following events, which do not require discontinuation:

- Grade 4 neutropenia ::; 7 days
- Grade 4 lymphopenia or leukopenia
- Isolated Grade 4 amylase or lipase abnormalities that are not associated with symptoms or clinical manifestations of pancreatitis
- Isolated Grade 4 electrolyte imbalances/abnormalities that are not associated with clinical sequelae and are corrected with supplementation/appropriate management within 72 h of their onset

Any drug-related Grade 4 endocrinopathy and Grade 3 adrenal insufficiency requires discontinuation.

Any event that leads to delay in dosing lasting> 8 weeks from the previous dose requires discontinuation, with the following exceptions:

- Dosing delays to allow for prolonged steroid tapers to manage drug-related AEs are allowed.
- Dosing delays lasting > 8 weeks from the previous dose that occur for non-drug-related reasons may be allowed if approved by the Lead Investigator.

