### Hematologic AEs:

- Absolute neutrophil count (ANC) < 500/mm^3 for more than 7 days
- Febrile neutropenia (a disorder characterized by an ANC < 1,000/mm^3 and single temperature 2: 38.3 °C or sustained temperature of 2: 38.0 °C for more than 1 h)
- Platelets < 25,000/mm^3
- Hemoglobin< 8.0 g/dL
- Grade 3 hemorrhage associated with thrombocytopenia less than Grade 4 (ie, grade 3 hemorrhage with platelets> 25,000/mm^3).

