### General:

- Interruption of ivosidenib dosing for more than a total of 2 weeks (not necessarily consecutive) during Cycle 1, if due to AEs related to ivosidenib.
- Delay of starting Cycle 2 for> 2 weeks, if due to AEs related to ivosidenib.

All safety data in Cycle 1 and subsequent cycles will be monitored on an ongoing basis.

A patient who experiences a DLT at any dose level will receive appropriate treatment and supportive

care as necessary and will be monitored closely until resolution of the AE to Grade Oto 1 severity or Baseline severity, whichever is more abnormal, or until the AE is stabilized at any acceptable grade.

Patients who experience a DLT but who, in the opinion of the Investigator, are deriving clinical benefit will be permitted to continue treatment with ivosidenib at a lower dose that has been demonstrated to be well tolerated upon reasonable resolution of the DLT.

AEs will be tabulated by type, severity, and attribution. Immune responses, as assessed at baseline, post ivosidenib lead in, and week 9 (first restaging) will be analyzed by mixed effects regression for longitudinal data. Baseline and post-treatment values will also be compared between responders and non-responders.

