# 8.2.4 Exploratory Objective: Biomarkers and Response to Treatment

DLT (defined in Section 7.5) will be monitored throughout the trial and a stopping rule will be evaluated after every five participants have started Cycle 1. If the number of participants experiencing DLT equals or exceeds the number specified in the following table, the trial will be paused and the dosing reconsidered:

# Participants	# DLTs
5	3
10	5
15	7
20	8
25	10
30	12

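### The laboratory exception in the DLT definition, as written, exempts abnormalities that do not resolve and counts those that do, and this definition feeds the toxicity stopping rule

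*Combined protocol and SAP*

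**What the plan says.** Section 7.5 limits DLTs to Cycle 1. After separate rules for nausea, vomiting and diarrhea, its non-hematologic list ends with a catch-all for any other Grade 3 or 4 event, "with the exception of asymptomatic amylase/lipase or other biochemical marker that does not resolve with adequate treatment and/or within a week".

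The other duration qualifiers in 7.5 are:

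- Nausea or vomiting without prophylaxis, and diarrhea without anti-diarrheals: each "is considered a DLT only if lasting> 3 days despite maximum supportive care".
- Neutrophils below 500/mm³: a DLT if this lasts "for more than 7 days".
- General criteria: "Interruption of ivosidenib dosing for more than a total of 2 weeks" in Cycle 1, or a delay of more than 2 weeks in starting Cycle 2, in both cases if due to ivosidenib-related events.

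Section 5.8, on stopping nivolumab, states: "Grade 3 drug-related AST, ALT, or total bilirubin requires discontinuation".

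Section 8.2.4 links the definition to the rule: "DLT (defined in Section 7.5) will be monitored throughout the trial and a stopping rule will be evaluated after every five participants". It continues: "If the number of participants experiencing DLT equals or exceeds the number specified in the following table, the trial will be paused". The boundaries are 3 of 5, 5 of 10, 7 of 15, 8 of 20, 10 of 25 and 12 of 30. No other section restates or corrects the exception.

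**The concern.** In the catch-all, the clause about not resolving directly follows the word marker, so it describes what is exempted. A Grade 3 or 4 asymptomatic abnormality that persists despite treatment then falls outside the DLT definition. One that clears in two days stays inside the catch-all and counts.

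DLT is a named secondary endpoint and the only count used by the formal toxicity rule. If the exception is applied as written, some events leave the count and others enter it. If investigators repair the sentence themselves, each repair gives a different count, and two centers are enrolling.

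**Working it through.** **Comparing the readings**

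| Event (Grade 3–4, non-hematologic) | Literal reading | Other parse: the clause on not resolving attaches to the whole catch-all |
|---|---|---|
| Asymptomatic marker, does not resolve | exempt | exempt |
| Asymptomatic marker, resolves | DLT | exempt |
| Other event in the catch-all, does not resolve | DLT | DLT |
| Other event in the catch-all, resolves | DLT | exempt |

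The literal reading runs against the two timed qualifiers in 7.5 (more than 3 days, more than 7 days), where persistence is what makes an event a DLT. It also sits uneasily with 5.8: a Grade 3 drug-related rise in AST, ALT or bilirubin ends nivolumab, yet if asymptomatic and persistent it would be exempt as another biochemical marker. The other parse restores the direction of the qualifiers, but it removes every resolving event in the catch-all from the DLT definition, laboratory or not. Under either parse, and/or leaves open whether failure to resolve with treatment, failure to resolve within a week, or both are required.

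**Reproducing the plan's rule**

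Inputs from 8.3: prior Beta(1, 4); pause when the posterior probability of a DLT rate above 0.3 exceeds 0.7. With x DLTs in n participants the posterior is Beta(1 + x, 4 + n − x). The smallest x that meets the criterion:

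| n | x | Posterior probability at x | At x − 1 |
|---|---|---|---|
| 5 | 3 | 0.730 | 0.463 |
| 10 | 5 | 0.781 | 0.584 |
| 15 | 7 | 0.818 | 0.666 |
| 20 | 8 | 0.725 | 0.565 |
| 25 | 10 | 0.771 | 0.636 |
| 30 | 12 | 0.807 | 0.693 |

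All six boundaries in 8.2.4 reproduce. An exact binomial recursion over the six looks gives P(pause) = 0.368 at a true rate of 0.30, which rounds to the stated 0.4. The mean number accrued given a pause is 11.9, which fits the stated 12. The rule's arithmetic is sound; the open question is which events enter it.

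**Sensitivity to the reading (assumed shifts)**

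The documents give no Cycle 1 rate of asymptomatic Grade 3–4 laboratory events. Let U be the share of participants whose only candidate event is a non-resolving marker, and R the share whose only candidate event is a resolving one. Let p be the DLT rate if U counts and R does not. This is a reference point only, not a proposal. The literal text then counts p − U + R.

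| p | U | R | Counted rate | P(pause) at p | P(pause) at counted rate |
|---|---|---|---|---|---|
| 0.30 | 0.05 | 0 | 0.25 | 0.37 | 0.20 |
| 0.30 | 0 | 0.05 | 0.35 | 0.37 | 0.56 |
| 0.30 | 0.10 | 0 | 0.20 | 0.37 | 0.09 |
| 0.30 | 0 | 0.10 | 0.40 | 0.37 | 0.74 |
| 0.20 | 0.10 | 0 | 0.10 | 0.09 | 0.01 |
| 0.20 | 0 | 0.10 | 0.30 | 0.09 | 0.37 |

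If U = R, the counted rate and P(pause) do not change, but different participants are counted.

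**The case against.** **The sentence may only be ambiguous.** The clause can be attached to the whole catch-all, so that unresolved events count, and a missing comma is weak evidence in text read from a PDF. That is fair as far as it goes: inversion is the literal reading, not the only possible one. But the other parse exempts all asymptomatic markers and all other resolving events in the catch-all, so it does not rescue the sentence.

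**Section 5.8 does not use the opposite logic throughout.** A reader might infer this from its exemption for abnormalities that "are corrected with supplementation/appropriate management within 72 h of their onset". That clause covers only isolated Grade 4 electrolyte abnormalities. Isolated Grade 4 amylase or lipase without symptoms or signs of pancreatitis is exempt there with no time condition. Section 5.8 also governs stopping nivolumab, not counting DLTs. This objection stands; only the liver-test provision creates a tension with the literal DLT text.

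**Other safeguards exist.** Ivosidenib-related interruptions or Cycle 2 delays of more than 2 weeks are DLTs in any case. Grade 3 or higher events and laboratory shifts are tabulated (8.2.2), and the monitoring bodies can suspend accrual (9.4). This also stands, but the backstop misses a persistent abnormality attributed to nivolumab, or one that does not hold ivosidenib that long.

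**The effect may be small.** Section 1.5 lists Grade 3 hyponatremia (5), hypophosphatasemia (5) and hyperglycemia (3) among 168 participants on ivosidenib, at most 13/168 = 7.7%. That is over all cycles and not limited to asymptomatic cases, so an assumed shift of 0.10 in Cycle 1 is high on those data. They do not include nivolumab's contribution, however, and list only events seen in more than two participants. At a rate of 0.20, losing a fifth of DLTs (0.20 × 0.8 = 0.16) moves P(pause) only from 0.09 to 0.04.

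**Conclusion.** The concern holds as a defect in one sentence of 7.5. Its literal meaning runs against the timed qualifiers around it, its alternative parse is a much wider exemption, and nothing elsewhere corrects it. Because 8.2.4 takes its count from 7.5, the stopping rule is not fully defined until the sentence is settled.

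Under the literal reading, only asymptomatic biochemical events are affected. With assumed shifts of 5 points around 0.30, P(pause) moves from 0.37 to 0.20 or 0.56. These figures show how steep the rule is near its threshold; they do not estimate the error.

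Three stronger inferences are not supported. One is that persistent toxicity in general goes uncounted: symptomatic events and the other DLT categories are untouched, and the 2-week criteria remain. Another is that the rule is biased in a known direction: under the literal reading unresolved events leave and resolved ones enter, and the two can offset. The third is that the centers do score events differently: the text allows it, but nothing in the documents shows it.

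**What to change.** Rewrite the exception in 7.5 so that it states which abnormalities are exempt (resolved or unresolved), the time limit, and whether the two conditions are joined by and or by or. Reconcile it with the other criteria in 7.5 and with the liver-test provision in 5.8, and apply that single reading to the 8.2.4 count at both centers. Which events should count is the sponsor's clinical decision.

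The cost is one sentence in an amendment. The boundaries in 8.2.4 do not change, because they depend only on the number of DLTs. If DLTs have already been scored, any Cycle 1 asymptomatic Grade 3–4 laboratory events should be checked against the clarified wording.

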### Hematologic AEs:

- Absolute neutrophil count (ANC) < 500/mm^3 for more than 7 days
- Febrile neutropenia (a disorder characterized by an ANC < 1,000/mm^3 and single temperature 2: 38.3 °C or sustained temperature of 2: 38.0 °C for more than 1 h)
- Platelets < 25,000/mm^3
- Hemoglobin< 8.0 g/dL
- Grade 3 hemorrhage associated with thrombocytopenia less than Grade 4 (ie, grade 3 hemorrhage with platelets> 25,000/mm^3).

### General:

- Interruption of ivosidenib dosing for more than a total of 2 weeks (not necessarily consecutive) during Cycle 1, if due to AEs related to ivosidenib.
- Delay of starting Cycle 2 for> 2 weeks, if due to AEs related to ivosidenib.

All safety data in Cycle 1 and subsequent cycles will be monitored on an ongoing basis.

A patient who experiences a DLT at any dose level will receive appropriate treatment and supportive

care as necessary and will be monitored closely until resolution of the AE to Grade Oto 1 severity or Baseline severity, whichever is more abnormal, or until the AE is stabilized at any acceptable grade.

Patients who experience a DLT but who, in the opinion of the Investigator, are deriving clinical benefit will be permitted to continue treatment with ivosidenib at a lower dose that has been demonstrated to be well tolerated upon reasonable resolution of the DLT.

AEs will be tabulated by type, severity, and attribution. Immune responses, as assessed at baseline, post ivosidenib lead in, and week 9 (first restaging) will be analyzed by mixed effects regression for longitudinal data. Baseline and post-treatment values will also be compared between responders and non-responders.

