## 2.2.2 Secondary Endpoints

- The occurrence of dose-limiting toxicity (DLT), as defined in Section 7.5, in patients receiving ivosidenib plus nivolumab.
- Adverse events in patients receiving the combination of ivosidenib and nivolumab based on CTCAEvS.0
- Progression Free Survival (PFS) Survival with freedom from objective tumor progression from time of first treatment until up to 18 months after the last participant has initiated treatment.

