# 5.9 Management of Nivolumab AEs

Participants should receive appropriate supportive care measures as deemed necessary by the treating investigator. Where appropriate, these guidelines include the use of oral or IV treatment with corticosteroids as well as additional anti-inflammatory agents if symptoms do not improve with administration of corticosteroids. Note that several courses of steroid tapering may be necessary as symptoms may worsen when the steroid dose is decreased. For each disorder, attempts should be made to rule out other causes such as metastatic disease or bacterial or viral infection, which might require additional supportive care. The treatment guidelines are intended to be applied when the investigator determines the events to be related to nivolumab.

It may be necessary to perform conditional procedures such as bronchoscopy, endoscopy, or skin photography as part of evaluation of the event.

- Pneumonitis:
  - For Grade 2 events, treat with systemic corticosteroids. When symptoms improve to Grade 1 or less, steroid taper should be started and continued over no less than 4 weeks.
  - o For **Grade 3-4 events**, immediately treat with IV steroids. Administer additional antiinflammatory measures, as needed.
  - o Add prophylactic antibiotics for opportunistic infections in the case of prolonged steroid administration.
- Diarrhea/Colitis:

Participants should be carefully monitored for signs and symptoms of enterocolitis (such as diarrhea, abdominal pain, blood or mucus in stool, with or without fever) and of bowel perforation (such as peritoneal signs and ileus).

- All participants who experience diarrhea/colitis should be advised to drink liberal quantities of clear fluids. If sufficient oral fluid intake is not feasible, fluid and electrolytes should be substituted via IV infusion. For Grade 2 or higher diarrhea, consider GI consultation and endoscopy to confirm or rule out colitis.
- o For **Grade 2 diarrhea/colitis** that persists greater than 3 days, administer oral corticosteroids.
- For **Grade 3 or 4 diarrhea/colitis** that persists> 1 week, treat with IV steroids followed by high dose oral steroids.
- o When symptoms improve to Grade 1 or less, steroid taper should be started and continued over no less than 4 weeks.
- o Type 1 diabetes mellitus (if new onset, including diabetic ketoacidosis [DKA]) or Grade 3 Hyperglycemia, if associated with ketosis (ketonuria) or metabolic acidosis (DKA)

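### Both treatment-limitation criteria in the DLT definition require an ivosidenib-related AE, so nivolumab-only toxicity below Grade 3 does not enter the combination's stopping rule

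*Combined protocol and SAP*

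**What the plan says.** Section 2.1.2 makes the safety of the combination a secondary objective. Section 2.2.2 names the endpoint as "The occurrence of dose-limiting toxicity (DLT), as defined in Section 7.5, in patients receiving ivosidenib plus nivolumab". Both drugs start on Day 1 of Cycle 1 (Section 3.1).

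The stem of Section 7.5 is neutral between the drugs: "A DLT is defined as any AE (except clearly attributable to an extraneous cause, such as disease progression) occurring in Cycle 1 (only"). So is the broad non-hematologic criterion, "Any other Grade 3 or 4 non-hematological AE, with the exception of asymptomatic amylase/lipase", and so are the hematologic criteria. The two General criteria differ. The first is about missed doses within the cycle: "Interruption of ivosidenib dosing for more than a total of 2 weeks (not necessarily consecutive) during Cycle 1, if due to AEs related to ivosidenib". The second is about a late start to the next cycle, and its wording names the same single drug: "Delay of starting Cycle 2 for> 2 weeks, if due to AEs related to ivosidenib".

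Section 5.8 lists reasons for permanent nivolumab discontinuation. One starts at Grade 2: "Any Grade 2 drug-related uveitis, eye pain, or blurred vision that does not respond to topical therapy" (with further conditions on recovery or need for systemic treatment). Section 5.5.1.1 has nivolumab withheld or stopped for a nivolumab-related safety issue and lets ivosidenib continue after consultation.

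Section 8.2.4 counts participants with a DLT as defined in Section 7.5. It pauses the trial at 3, 5, 7, 8, 10 or 12 DLTs among 5, 10, 15, 20, 25 or 30 participants. Section 8.3 derives these limits from a beta-binomial model with prior Beta(1,4) and a posterior probability above 0.7 that the DLT rate exceeds 0.3.

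**The concern.** The General criteria are the only part of the definition that asks whether toxicity limited treatment, as opposed to reaching a grade or a laboratory value. Restricting them to one drug leaves an asymmetry. A Cycle 2 delay of more than 2 weeks is a DLT when the cause is judged related to ivosidenib and is not when the cause is judged related to nivolumab only. Permanent loss of nivolumab in Cycle 1 for a Grade 2 event meets no criterion at all if ivosidenib continues on time.

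The stopping rule is the plan's formal sequential check on the tolerability of the pair, and it sees only what Section 7.5 counts. If such events occur, the rule reacts to a lower rate than the rate at which treatment is actually limited.

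**Working it through.** **Step 1: follow one event through the definition.** Take the Grade 2 eye event of Section 5.8, in Cycle 1, judged related to nivolumab and not to ivosidenib.

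| Part of Section 7.5 | Met? | Reason |
|---|---|---|
| Stem | Yes | Cycle 1 AE without a clearly extraneous cause |
| Non-hematologic criteria | No | All need Grade 3 or 4 |
| Hematologic criteria | No | Not a blood-count, febrile-neutropenia or hemorrhage event |
| General, interruption | No | Concerns ivosidenib dosing and ivosidenib-related AEs |
| General, Cycle 2 delay | No | Ivosidenib-related AEs only |

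The event forces permanent discontinuation of one study drug and adds nothing to the count. This needs no numerical assumption. Section 5.8 also lists a combined transaminase and bilirubin trigger separately from its Grade 3 liver trigger. Whether that combination can occur below Grade 3 depends on CTCAE limits that the documents do not reproduce, so I do not rely on it.

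**Step 2: reproduce the plan's boundaries.** At each look of size n, find the smallest k with P(p > 0.3) > 0.7 under Beta(1 + k, 4 + n − k).

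| n | Boundary k | Posterior at k | Posterior at k − 1 |
|---|---|---|---|
| 5 | 3 | 0.730 | 0.463 |
| 10 | 5 | 0.781 | 0.584 |
| 15 | 7 | 0.818 | 0.666 |
| 20 | 8 | 0.725 | 0.565 |
| 25 | 10 | 0.771 | 0.636 |
| 30 | 12 | 0.807 | 0.693 |

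All six agree with Section 8.2.4.

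**Step 3: probability of a pause.** Let f_j(k) be the probability of k DLTs at look j with no earlier crossing. Then f_j(k) = Σ_x f_{j−1}(k − x) · C(5,x) p^x (1 − p)^(5−x), and P(pause) = Σ_j Σ_{k ≥ r_j} f_j(k), where r_j is the boundary at look j. For example, the first look at p = 0.40 contributes 10(0.4³)(0.6²) + 5(0.4⁴)(0.6) + 0.4⁵ = 0.230 + 0.077 + 0.010 = 0.317.

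| Counted DLT rate | 0.20 | 0.25 | 0.30 | 0.35 | 0.40 |
|---|---|---|---|---|---|
| P(pause) | 0.094 | 0.204 | 0.368 | 0.560 | 0.740 |

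Section 8.3 gives 0.4 at a rate of 0.3. The exact value, 0.368, agrees to one decimal. Its expected accrual of 12 agrees with the mean conditional on a pause (11.9); the unconditional mean is 26.5 with a maximum of 35.

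**Step 4: effect of uncounted events, by assumption.** Let T be the rate of all treatment-limiting Cycle 1 toxicity and u the part that Section 7.5 does not count. The rule then acts on T − u. The documents give no value for u, so a range is shown.

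| u | P(pause), T = 0.30 | P(pause), T = 0.40 | Mean accrual, T = 0.40 (maximum 35) |
|---|---|---|---|
| 0 | 0.368 | 0.740 | 18.0 |
| 0.03 | 0.264 | 0.636 | 20.5 |
| 0.05 | 0.204 | 0.560 | 22.3 |
| 0.10 | 0.094 | 0.368 | 26.5 |

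**The case against.** Much can be said for the plan.

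- **Coverage of nivolumab.** A reader might infer that the rule misses nivolumab toxicity altogether. It does not: Grade 3 or 4 events in Cycle 1 count whichever drug caused them, subject to the listed exceptions.
- **Attribution.** A reader might infer that, with concurrent dosing, whether an event counts is arbitrary. Section 7.1.5 sets a low bar, a reasonable possibility of causation, and Table 5 has a category for possibly related events. A truly ambiguous event can therefore count towards ivosidenib if it interrupts ivosidenib or delays Cycle 2 for long enough. The remark in Section 5.7 that the responsible drug can be hard to identify concerns infusion reactions only.
- **Steroid tapers.** For several Grade 2 immune events Section 5.9 says "When symptoms improve to Grade 1 or less, steroid taper should be started and continued over no less than 4 weeks". A reader might infer that Cycle 2 is then delayed beyond 2 weeks. Section 5.9 does not make Cycle 2 wait for the taper, and Section 5.5.1.1 allows ivosidenib to continue. The clear case is the Grade 2 eye event in Section 5.8.
- **Bias.** A reader might call the reported DLT rate biased. The endpoint is defined by reference to Section 7.5, so the rate matches it by construction. What is open to question is whether that definition suits a combination.
- **Design reason.** Only ivosidenib has a lower dose level (Section 3.1), and nivolumab dose changes are not permitted (Section 5.5.1.1). Tying the delay criteria to the adjustable drug is a possible rationale, but the documents do not give it, and it fits poorly with the drug-neutral Grade 3 and 4 criteria.
- **Other safeguards.** Safety data are monitored throughout (Section 7.5), the DSMB and DSMC can suspend accrual (Section 9.4), and AEs leading to dose modification or discontinuation are tabulated (Section 8.2.2).

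These points narrow the gap. They do not close it for a sub-Grade 3 event judged related to nivolumab only.

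**Conclusion.** The point holds in a limited form. A Cycle 1 event that meets no grade or laboratory criterion and is judged related to nivolumab only cannot be a DLT, even when the protocol requires nivolumab to be stopped permanently. Such events are missing from the formal stopping count, not from safety review. This follows from the wording of Sections 5.8, 7.5 and 8.2.4 alone.

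The size is unknown. The loss in P(pause) at a true rate of 0.40 is 0.740 − 0.636 = 0.10, 0.740 − 0.560 = 0.18 or 0.740 − 0.368 = 0.37 for 3, 5 or 10 uncounted points. These points are illustrative, and none should be read as an estimate for this trial.

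One further effect is possible. Section 8.1.1 ties safety evaluability to at least 75% of Cycle 1 ivosidenib unless a DLT occurs. A participant who falls short because of a nivolumab-only Grade 2 event would be neither a DLT nor safety-evaluable, and so might also leave the denominator.

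**What to change.** Reconcile Section 7.5 with Sections 2.2.2, 5.5.1.1, 5.8 and 8.2.4:

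1. In both General criteria, let the attribution refer to study treatment, meaning either drug or the combination.
2. Have the sponsor state whether discontinuation of nivolumab in Cycle 1, or delay of its next dose because of a Cycle 1 AE, counts as a DLT. Step 1 alone does not settle this: nivolumab stopped for good while ivosidenib continues on time would still meet neither criterion. The choice and any threshold are clinical and belong to the sponsor.
3. Reconcile the Section 7.5 sentence on continuing ivosidenib at a lower dose after a DLT with Section 5.5.1.1, and state its scope. DLT status affects management through that sentence, and through the reconsideration of dosing in Section 8.2.4, so widening the definition is not purely a matter of counting.
4. If the ivosidenib-only restriction is intended, say so, give the reason, and describe the endpoint and stopping rule accordingly.

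The cost is a few sentences and a higher chance of a pause. If the counted rate rises from 0.20 to 0.25, P(pause) rises from 0.09 to 0.20; at 0.30 it is 0.37. The boundaries follow from the model whatever is counted, but the sponsor should confirm that the 0.3 limit and the Beta(1,4) prior still suit the wider definition.
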